### 7.3.2.2 Study data from medical records

The medical record search for data extraction can start in parallel to the questionnaires/survey being answered.

Data to be collected from the medical records include:

- Demographics and hearing/device history information
- Pre- and post-primary tympanoplasty air and bone conduction audiograms (unaided and when applicable aided and PTA4 at minimum)
- Latest available (as per inclusion criteria) air and bone conduction audiograms (unaided and when applicable aided and PTA4 at minimum)
- COM-related contacts with health care providers for the operated ear (including name and number of interventions and/or procedures, medications and therapies, examinations and Middle Ear Risk Index factors and surgical outcomes where applicable)

More details on the information to be collected can be found in **Appendix 1**.

It might be the case in a few sites, that the required audiograms for some subjects were collected in a hearing aid partner centre/shop and not in the clinic itself. For these situations, clinics will reach out to the responsible audiologist and request a copy of the test.

For analysis, health care contacts, interventions and/or procedures will be coded using the ICD-10 coding system. Medication will be coded according to WHO CC ATC.

## 7.4 Safety Evaluations and Procedures

Not applicable.

### 7.4.1 Concomitant Medication and Therapies

All medications and therapies related to COM and its rehabilitation which were prescribed during and from primary tympanoplasty must be recorded in the appropriate section of the eCRF.

## 7.5 Equipment Used for Evaluation of Performance and Safety

Not applicable.

## 7.6 Sponsor Role in Conduct of the Clinical Investigation

The Sponsor employees (or designee) shall use standard operating procedures to ensure that clinical study procedures and documentation are consistently conducted and compliant with Declaration of Helsinki and applicable parts of GCP and any regional or national regulations.

The Sponsor shall ensure that the study is quality controlled (monitored) by a monitor who is independent from the study, scientifically and clinically competent and has good knowledge of the study plan, ICF, sponsor's SOPs, GCP and applicable laws and regulations.

The Sponsor shall monitor tasks delegated to other organizations/persons (Sponsors oversight) e.g. contract research companies (CRO) or other consultants.

The Sponsor is responsible for developing a study plan and compile a clinical study report when the study is completed.

The Sponsor shall make sure that electronic systems used in the study are validated, that a Trial Master File is created, subjects identity are coded so that reported data is coded but can be linked to the respective research person, that all essential study documentation is available in a safe place before, during and after the study according to applicable laws and regulations.

The Sponsor shall also make sure that the investigators have sufficient qualifications, enough resources are available at site, collect signed study plans from respectively responsible investigator and establish agreements with participating clinics.

It is the Sponsor's responsibility to check that there is an EC approval for the study, to register the study in a public database and assure that the study results are reported within one year.

All study deviations will be documented in the CRF to enable analysis and reporting by the Sponsor in the Study Report, or to the relevant regulatory authority(s), if applicable.

## **8 RISKS AND BENEFITS OF THE INVESTIGATIONAL MEDICAL DEVICE AND CLINICAL INVESTIGATION**

### **8.1 Anticipated Clinical Benefits**

Participation in this study will not directly benefit the subject nor will it alter the subject's course of care. However, information gained from the study may identify shortcomings in the current standard of care, which may be used to guide more effective interventions in the future.

Additionally, by collecting self-reported feedback via the questionnaires from the subjects, the clinical personnel can take the opportunity to identify potential needed follow-ups accordingly.

### **8.2 Anticipated Adverse Device Effects**

Not applicable.

### **8.3 Risks Associated with Participation in the Clinical Investigation**

Participation in the study will not alter the subject's course of care. Sensitive data concerning the subject's health is being handled in the study. For subjects completing the ICF and questionnaires/survey at home, there is a risk that these documents might be lost in transit.

### **8.4 Risk Mitigation**

All data collected will be pseudonymised and therefore the risk that any sensitive data will be disclosed to unauthorized persons is considered to be minimal. Registered post will be used when

sending ICFs and questionnaires/survey. For questionnaires/survey, clinical personnel will complete header with subject identification code and request that no personal data is shared on these documents, making them pseudonymised.

## 8.5 Risk-to-Benefit Rationale

The benefit of the clinical investigation of potentially identifying shortcomings in the standard of care and hence being able to guide more effective interventions in the future is regarded to outweigh the minimal anticipated risk for the subjects participating in the clinical investigation. We therefore consider it ethical to conduct the investigation.

# 9 STATISTICAL CONSIDERATIONS

## 9.1 General Considerations

Descriptive statistics will be used for analysis in this study. All analyses will be made on the full data set. All analyses will be presented as aggregated data without the possibility of identifying data from individual subjects.

## 9.2 Endpoints

### 9.2.1 Primary Endpoint

1. Categorical data collected from primary tympanoplasty to time of enrolment:
  - Number and type of contacts with health care providers
  - Number and type of interventions and/or procedures (medical examinations, surgical procedures, hearing rehabilitation)
  - Number and type of medications and therapies

### 9.2.2 Secondary Endpoints

1. Pre- and post-primary tympanoplasty and a third assessment between 2018 and point of enrolment:
  - PTA4 (0.5, 1, 2 and 4 kHz) for both air and bone conduction, under unaided and when applicable aided conditions.
2. From primary tympanoplasty to time of enrolment (analysed in patient-years):
  - Unit cost
3. At time of enrolment:
  - Client Service Receipt Inventory (CSRI)
4. At time of enrolment:
  - Health Utilities Index Mark III (HUI3)
  - Chronic Otitis Media Outcome Test-15 (COMOT-15)
  - Speech, Spatial and Qualities of Hearing Scale (SSQ-12)
5. Responses from a minimum of 30 subjects per language and audiograms collected within one year of questionnaire completeness.

### 9.2.3 Exploratory Endpoints

1. Middle Ear Risk Index factors (preoperative status, intraoperative findings) and surgical outcomes, if available.
2. Data on employment status collected in the CSRI survey used to determine the number of lost working hours as a result of COM.

## 9.3 Hypotheses

### 9.3.1 Primary Hypothesis

Not applicable.

### 9.3.2 Secondary Hypothesis

Not applicable.

### 9.3.3 Exploratory Hypothesis

Not applicable.

## 9.4 Sample Size Determination

The aim of this investigation is to map health care utilised by subjects with a history of COM, who have already had a primary tympanoplasty. Findings from this investigation will primarily help estimate the burden in terms of health care costs and impact on HRQoL that follows a first tympanoplasty for this subject population. As this study is not testing for differences in treatments or strengths of associations (primary objective is to map healthcare utilisation) then it is only necessary that the study is capable of capturing all potential interventions that may be offered as standard of care for the population. To ensure that enough medical records are sampled to capture all potential COM-related interventions included in the standard of care a sample size determination using published methods for calculating sample sizes in retrospective studies was undertaken (39). The calculation is based on the potential for patients with COM to receive the least likely intervention, which was determined to be a bone conduction solution, prescribed at a rate of 2.63% (unpublished registry data). Using these data, we estimate that 200 subjects are sufficient to capture the least likely intervention in at least four subjects, where the probability of observing this intervention at least once is 98% with a 95% confidence interval of 96-100% (Table 1).

Table 1. Expected number of subjects receiving treatment according to sample size.

		Results: Expected number of individuals receiving treatment; (Probability of observing treatment at least once); ± Expected 95% confidence interval width for proportion receiving treatment					
		Sample size					
		50	100	200	300	500	1000
Proportion receiving treatment	0,01	1 (0,39); +/-0,03	1 (0,63); +/-0,02	2 (0,87); +/-0,01	3 (0,95); +/-0,01	5 (0,99); +/-0,01	10 (1); +/-0,01
	0,02	1 (0,64); +/-0,04	2 (0,87); +/-0,03	4 (0,98); +/-0,02	6 (1); +/-0,02	10 (1); +/-0,01	20 (1); +/-0,01
	0,04	2 (0,87); +/-0,05	4 (0,98); +/-0,04	8 (1); +/-0,03	12 (1); +/-0,02	20 (1); +/-0,02	40 (1); +/-0,01
	0,08	4 (0,98); +/-0,08	8 (1); +/-0,05	16 (1); +/-0,04	24 (1); +/-0,03	40 (1); +/-0,02	80 (1); +/-0,02
	0,16	8 (1); +/-0,1	16 (1); +/-0,07	32 (1); +/-0,05	48 (1); +/-0,04	80 (1); +/-0,03	160 (1); +/-0,02
	0,32	16 (1); +/-0,13	32 (1); +/-0,09	64 (1); +/-0,06	96 (1); +/-0,05	160 (1); +/-0,04	320 (1); +/-0,03

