## 9.6 Primary Endpoint Analyses

COM-related health care utilisation, collected from medical records, from date of primary tympanoplasty to point of enrolment (analysed in patient-years) and CSRI questionnaire referring to the six-months prior to completion will be cross-checked to ensure data accuracy. Any overlapping extracts will be analysed as a single extract. Data from medical records related to information on health care contacts and costs for each contact (detailed variables are presented below) will be used in the analysis. Care consumption in the form of contacts, diagnoses and costs will be analysed with a view to identifying cost factors. All comparisons will be presented as aggregated data without the possibility of identifying data for individual subjects. Data coding will permit care episodes (a series of care contacts of the same individual) to be identified so that health care consumption and costs can be calculated per individual subject.

Health care utilisation will be mapped per individual subject and sub-analysis will be performed based on intervention subtypes, if feasible.

Health care contacts, interventions and/or procedures will be coded by ICD-10 classification. Medications will be summarised by higher level anatomical therapeutic classification (ATC) group and generic term. Therapies will be listed but not coded.

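### Section 9.4 states an expected count of four as a minimum, and attaches the margin for the treated proportion to the 98% detection probability

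*Combined protocol and SAP*

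**What the plan says.** Section 9.4 sets the aim of the sample size: since no differences or associations are tested, "it is only necessary that the study is capable of capturing all potential interventions" in the standard of care. The rarest of these is taken to be a bone conduction solution, "prescribed at a rate of 2.63% (unpublished registry data"). From this the section concludes that "200 subjects are sufficient to capture the least likely intervention in at least four subjects". It then puts the chance of one or more recipients at 98%, adds to that figure a "95% confidence interval of 96-100" per cent, and refers to Table 1.

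Each cell of Table 1 holds three numbers, defined in its header:

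- "Expected number of individuals receiving treatment";
- the probability of seeing the treatment at least once;
- a ± value, the "Expected 95% confidence interval width for proportion receiving treatment".

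The table has rows for 1%, 2%, 4%, 8%, 16% and 32%, and none for 2.63%. For 2% and n = 200 the cell reads 4, (0.98), ±0.02. These are the figures that the sentence uses.

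Section 9.6 adds that "sub-analysis will be performed based on intervention subtypes, if feasible".

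**The concern.** Two of the three numbers change meaning between the table and the sentence.

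- **Count.** An average over repeated samples becomes a number of subjects that the study will reach or exceed.
- **Interval.** A margin for the share of subjects treated becomes a margin for the chance of detecting the treatment.

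The sentence is the plan's summary of why 200 subjects are enough. Taken at face value, it promises four or more bone conduction users and a detection probability known to within 2 points. The first matters most for the sub-analysis by intervention subtype in section 9.6, because whether that is feasible depends on how many users are likely to appear.

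**Working it through.** **Inputs (section 9.4 and Table 1):** n = 200; p = 0.02 (the row used) and p = 0.0263 (the rate cited); 95% two-sided confidence, z = 1.96. The number of recipients X is taken as binomial(n, p).

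**Step 1. Reproduce the plan's cell (p = 0.02, n = 200).**

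- Expected count: n·p = 200 × 0.02 = 4.0
- Detection: 1 − (1 − p)^n = 1 − 0.98^200 = 0.9824
- Wald half-width for p: 1.96 × √(0.02 × 0.98 / 200) = 0.0194

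These round to 4, 0.98 and ±0.02, as printed. The other cells of Table 1 also reproduce to rounding. The printed ± is numerically a half-width.

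**Step 2. The probability of four or more.** P(X ≥ 4) = 1 − Σ P(X = k), k = 0 to 3.

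- p = 0.02: 1 − (0.0176 + 0.0718 + 0.1458 + 0.1963) = 0.5685
- p = 0.0263: 1 − (0.0048 + 0.0262 + 0.0703 + 0.1253) = 0.7734

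Three or fewer recipients therefore occur with probability 43% or 23%.

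**Step 3. The same figures at both rates, n = 200.**

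| | p = 2% | p = 2.63% |
|---|---|---|
| Expected count | 4.0 | 5.26 |
| P(at least one) | 98.2% | 99.5% |
| P(at least four) | 56.9% | 77.3% |
| 2.5th to 97.5th percentile of the count | 1 to 8 | 1 to 10 |
| Probability within that range | 96.2% | 97.8% |
| Wald half-width for p | 1.94 points | 2.22 points |
| Wald interval for p | 0.06% to 3.94% | 0.41% to 4.85% |

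With the permitted 10% over-recruitment (n = 220), P(at least four) is 64% at 2% and 83% at 2.63%.

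**Step 4. Which quantity the ±0.02 belongs to.** 0.98 − 0.02 = 0.96 and 0.98 + 0.02 = 1.00, which is the interval in the text. The table header assigns the ± to the treated proportion, and step 1 confirms it, since the formula with p = 0.02 returns 0.0194.

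Three cells print the same expected count of 4 and detection probability of 0.98, but different margins:

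| n | p | Half-width for p | Printed ± | 0.98 ± printed value |
|---|---|---|---|---|
| 200 | 2% | 0.0194 | 0.02 | 96-100% |
| 100 | 4% | 0.0384 | 0.04 | 94-102% |
| 50 | 8% | 0.0752 | 0.08 | 90-106% |

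The margin follows the precision of p, which differs between these cells, while the detection probability is the same.

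**Step 5. Scale, if uncertainty in p were carried into the detection probability.** As an illustration only, putting the Wald limits of step 3 into 1 − (1 − p)^200 gives about 11% to 100% at 2% and 56% to 100% at 2.63%. This treats the rate as if it had been estimated from 200 subjects. The plan does not give the size of the registry behind the 2.63%, so these are not proposed as replacement intervals.

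**The case against.** **At least four may be a floor on the expectation.** The cited rate lies above the 2% row, so the expected count (5.26) is indeed at least four. The sentence is framed as an estimate and points to a table of expected numbers. This reading is possible and may be what was meant. The text does not say so, however: it speaks of subjects captured and does not state that the 2% row was used as a conservative case. On this half the fault is wording that is wrong if read literally.

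**A Wald interval around 0.98 with n = 200 has the same half-width.** It does, because p(1 − p) is the same for 0.02 and 0.98. But 0.98 is not a proportion observed in 200 subjects, and the table assigns the margin elsewhere.

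**Crossing 100% proves little.** Fair. Wald margins cross their bounds under the correct reading too: the 1% row at n = 50 gives 1% ± 3 points. The proof is the header and the formula; the three cells only illustrate it.

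**Nothing depends on four.** Largely right. The stated aim is to see each intervention at least once, no rule requires four recipients, and the subtype analysis is conditional on feasibility with no threshold. Table 1 stands beside the sentence with its terms correctly defined. This limits the consequence but does not make the sentence correct.

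**Conclusion.** The point holds as a reporting error in the sample-size justification. The 96-100% interval is attached to the wrong quantity; the margin is about ±2 points on the treated proportion. Four is an expected count at 2%, and the chance of reaching it is 57% at 2% or 77% at 2.63%.

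N = 200, Table 1 and the 98% are correct, and the aim of observing the rarest intervention at least once is met. Using the 2% row for a rate of 2.63% is conservative and needs only to be stated. For judging the subtype analyses, the realistic range is 1 to 8 users at 2%, or 1 to 10 at 2.63%, each covering at least 95% of samples.

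These figures assume independent subjects with a common rate, and that the registry rate applies to the enrolled population.

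**What to change.** Keep N = 200 and Table 1, delete the interval around 98%, and replace the summary sentence. Two versions would do.

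*At the cited rate:* With 200 subjects and a rate of 2.63%, the expected number receiving a bone conduction solution is 5.3. The probability of at least one is 99.5%, and of at least four 77%. The expected 95% confidence interval for the proportion is about 2.6% ± 2.2 points (Wald).

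*At the tabulated rate:* Taking the 2% row of Table 1 as a conservative case, four recipients are expected. The probability of at least one is 98%, and of at least four 57%. The 95% half-width for the proportion is about 2 points.

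An exact interval could be added for context: 0.8% to 5.7% if 5 of 200 are observed. The probability of at least four may be left out if four has no role in the plan; calling the count expected is the necessary change.

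The cost is one sentence, with no extra subjects or analyses, and a less favourable statement about four users. Section 18 requires a documented amendment notified to the ethics committees. Version 4.0 was signed in December 2022 and recruitment was planned to end in Q1 2023, so the change is best combined with any other amendment. If none follows, the clinical investigation report should carry the corrected statement.

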## 9.5 Analysis Populations

Full analysis set consists of all subjects enrolled in the study.

## 9.6 Primary Endpoint Analyses

COM-related health care utilisation, collected from medical records, from date of primary tympanoplasty to point of enrolment (analysed in patient-years) and CSRI questionnaire referring to the six-months prior to completion will be cross-checked to ensure data accuracy. Any overlapping extracts will be analysed as a single extract. Data from medical records related to information on health care contacts and costs for each contact (detailed variables are presented below) will be used in the analysis. Care consumption in the form of contacts, diagnoses and costs will be analysed with a view to identifying cost factors. All comparisons will be presented as aggregated data without the possibility of identifying data for individual subjects. Data coding will permit care episodes (a series of care contacts of the same individual) to be identified so that health care consumption and costs can be calculated per individual subject.

Health care utilisation will be mapped per individual subject and sub-analysis will be performed based on intervention subtypes, if feasible.

Health care contacts, interventions and/or procedures will be coded by ICD-10 classification. Medications will be summarised by higher level anatomical therapeutic classification (ATC) group and generic term. Therapies will be listed but not coded.

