# 7 DESIGN OF THE CLINICAL INVESTIGATION

## 7.1 General

This is *primarily a retrospective study* to evaluate the standard of care of patients with COM across three countries in Europe. The study is therefore set up as a multicentre clinical investigation with a retrospective part (medical record review) and a minor prospective element with questionnaires and a survey completed by the subjects.

**Figure 1:** Schematic illustration of the clinical investigation elements

The subjects shall include men and women aged 18 years or older who underwent primary tympanoplasty to improve hearing between 2010-2016 and have a historically documented diagnosis of COM, with or without cholesteatoma in the operated ear. Subjects will be screened and 200 subjects will be enrolled in the clinical investigation across the 6-9 investigation sites in Germany, Spain and France. The study will aim to enrol subjects with an even distribution across all study sites. If any site has difficulties with recruitment the remaining sites can recruit more subjects, so the total recruitment is not affected, upon agreement with the Sponsor. In view of a possible situation where last recruitment efforts may result in exceeding the needed 200 subjects, no more than 10% over recruitment is expected.

In case no other follow-up visit to the clinic is planned within the study recruitment period subjects who have had an audiogram done between 2018 and the point of enrolment will be sent the ICF, questionnaires and survey via registered mail for completion at home. Subjects who are planned to have a follow-up audiogram collected within the study recruitment period will be asked to complete the ICF, questionnaires and survey at the time of their appointment. The medical record search for data extraction will be done at the clinic. See section 3. *Schedule of Events*.

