#### Health care utilisation survey

The Adapted version of the Client Service Receipt Inventory (CSRI) (32), is a research instrument developed in the mid-1980s to collect information on primarily service utilisation and has been used in over 500 studies.

The CSRI can be used at multiple points within a study, thus tracking changes over time. The CSRI is also adaptable in administration. Although originally designed to be administered to the service user or their carer face to face with a trained interviewer, the CSRI has been successfully administered via post for the service user to be completed by themselves.

The adapted version of CSRI will, in this investigation, collect data referring to the 6 months before enrolment regarding demographics (marital status, cohabitation, usual place of residence, education level), medical history (chronic diseases, smoking status, date when first diagnosed with chronic ear infection, current middle ear issues, recurrent ear infections), hearing rehabilitation (current hearing aid or hearing device and category of hearing aid/device and hours per day of usage if applicable), health care utilisation related to ear infection and hearing difficulties (number of face-to-face consultations with care providers, investigations or diagnostic tests, number of in-patient admissions, medications) and employment information (employment status, inability to work in days/hours).

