### Health Care Contacts – COM-related only for the operated ear

Type of contact

Reason for contact/procedure

DRG Code

Start date

End date

Care provider

Inpatient days

Ear

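### Apart from a six-month survey and requested audiograms, the plan has no step to obtain COM-related care given outside the study clinic, so primary utilisation and cost may be understated by an unreported amount

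*Combined protocol and SAP*

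**What the plan says.** Section 9.2.1 words the first component of the primary endpoint as "Number and type of contacts with health care providers", alongside procedures (including hearing rehabilitation) and medications and therapies. Section 7.3.2.2 narrows what is collected to "COM-related contacts with health care providers for the operated ear", and Appendix 1 repeats the limit: "Health Care Contacts – COM-related only for the operated ear". These limits concern the disease and the ear. None of them restricts the endpoint to one provider.

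On the source, section 7.1 states "The medical record search for data extraction will be done at the clinic", and the Schedule of Events assigns the task to site personnel. Section 9.6 then says that "Data from medical records related to information on health care contacts and costs for each contact" will be used in the analysis. It also brings in the survey: "CSRI questionnaire referring to the six-months prior to completion will be cross-checked to ensure data accuracy". Entries found in both sources are to be merged and counted once. Nothing is said about entries found in only one.

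The CSRI asks for the "number of face-to-face consultations with care providers", plus tests, admissions and medications for ear infection and hearing difficulties, over six months and without restriction to the study clinic (section 7.3.2.1).

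The only outside retrieval is in section 7.3.2.2. It allows that at a few sites "the required audiograms for some subjects were collected in a hearing aid partner centre/shop and not in the clinic itself", and asks the audiologist for a copy of the test. Inclusion criterion 11 requires record data over the whole search period but does not say which providers' records are meant.

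**The concern.** The endpoint is defined by disease and ear, while the source is defined by place. Every subject has been advised to try a hearing aid (criterion 6), so hearing rehabilitation matters for the whole sample, and some of it may happen outside the clinic. The same holds for routine ear care and prescriptions from other providers. Such care enters the count only if it left a trace in the clinic file.

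This bears on the study's main product. Section 9.4 makes the ability to capture every intervention in the standard of care the design requirement. Section 9.7 builds costs on the utilisation counts and uses study data to decide when subjects reach a stable state. If care moved out of the clinic over time, a falling clinic count could look like stability. As written, the report would carry no measure of how complete the count is.

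**Working it through.** **1. The plan's own completeness figure.** Section 9.4 and Table 1 give a 98% chance of seeing the least likely intervention at least once in 200 subjects.
- At the Table 1 rate: 1 - (1 - 0.02)^200 = 0.982, expected count 200 × 0.02 = 4. This reproduces.
- At the 2.63% in the text: 1 - (1 - 0.0263)^200 = 0.995, expected count 5.26.

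Both presume that an intervention which was given is found in the data. The point below does not depend on this figure.

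**2. Length of follow-up.** Inputs: surgery 2010-2016 (criterion 4) and recruitment Q1 2022 to Q1 2023 (synopsis).
- Shortest: 31 Dec 2016 to 1 Jan 2022 = 5.0 years, which agrees with the five-year minimum in section 7.1.1.
- Longest: 1 Jan 2010 to 31 Mar 2023 = 13.2 years.

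**3. Share of follow-up with a second source of contacts.** CSRI window / follow-up = 0.5 / T.
- T = 5.0: 10.0%. T = 13.2: 3.8%.
- The clinic record is the only planned source for the other 90.0% to 96.2%, that is 4.5 to 12.7 years per subject. Recruitment works backwards from 2016 (section 7.2.5), so many subjects should lie nearer the short end.

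**4. Possible size.** The documents give no share of care outside the clinic, so I assume a range. Let s be the share of COM-related care that was given elsewhere and is not documented at the clinic, with a constant contact rate.
- Record only: captured share = 1 - s.
- Record plus fully captured CSRI contacts in the last six months: (1 - s) + s × 0.5 / T.

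| s (assumed) | Record only | Record plus CSRI, T = 13.2 to 5.0 |
|---|---|---|
| 10% | 90% | 90.4% to 91.0% |
| 30% | 70% | 71.1% to 73.0% |
| 50% | 50% | 51.9% to 55.0% |

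Adding CSRI-only contacts therefore recovers little. It would also create an artificial step: at s = 30%, the last six months would show 1 / 0.7 = 1.43 times the earlier rate with no change in care.

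**5. What the shared six months can support.** Assume one CSRI-reported contact per subject (200 in all) and a captured share of 0.7.
- Pooled: 1.96 × sqrt(0.7 × 0.3 / 200) = 0.064, or about ±6 points.
- Split by 3 countries and an assumed 5 provider types: 200 / 15 ≈ 13 contacts per cell, and 1.96 × sqrt(0.7 × 0.3 / 13.3) ≈ 0.25, or about ±25 points.

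Both widths are optimistic. They need contact-by-contact matching and independent contacts, whereas the CSRI is described as giving counts, and contacts cluster within subjects. A ratio of two counts is not a binomial proportion and can exceed 1. Pooled agreement is usable; cell-by-cell scaling is not.

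**The case against.** The best defence is that this is a descriptive retrospective study with no hypotheses, and that several provisions support completeness. Criterion 11 requires record data throughout. Appendix 1 has fields for care provider and type of contact, so the data set is not confined by design to care delivered at the clinic. It also collects device type, name and dates of use and hearing aid history, so device use is at least partly covered. Clinic files may contain letters from other providers. The partner-centre remark concerns audiograms for some subjects at a few sites. Section 9.6 does pair the records with the CSRI, and its rule on overlaps can be read as combining two sources.

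Most of this stands, and it limits the point. A reader might infer that every contact is counted solely from the operating hospital's files and that all other care is lost over the whole follow-up. The documents do not support that: collection is restricted to COM-related care of the operated ear, the plan says only that the search is at the clinic, the CSRI covers the last six months, and outside care may be documented in the file. A reader might also infer that the rate is shown to be biased downward, or that a planned country comparison is confounded. No capture share is given, no country comparison of utilisation is specified, and the base-case costing pools utilisation.

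The defence does not close the gap. A provider field records what the clinic knows; it does not supply outside records. Criterion 11 cannot assure completeness without naming whose records it means, and the treatment of CSRI-only contacts remains unstated.

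**Conclusion.** Capture of COM-related care outside the study clinic is not assured for about 90-96% of the observation time, and the plan reports no measure of what is lost. Utilisation and cost per patient-year may be understated, and the extent may vary by site. The size is unknown: 10%, 30% and 50% are illustrations that follow directly from the assumed s, not estimates. The 90-96% rests on the stated surgery and recruitment windows and on the CSRI being the only second source of contacts.

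This should be fixed before analysis because it determines what the primary result can be said to measure. It does not invalidate the study: as a description of care documented at the clinic, the planned data stand.

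**What to change.** In section 9.6:

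1. For the six months that both sources cover, report total CSRI-reported and clinic-recorded contacts as a ratio of counts (clinic / CSRI), with a confidence interval from a bootstrap that resamples subjects. Give it pooled, and descriptively by broad provider type and by country. Use the same dates and the same kind of contact in both sources: section 7.3.2.1 counts the six months back from enrolment, section 9.6 from completion, and the CSRI asks about face-to-face consultations. State that the CSRI is self-reported, does not separate ears and is not a gold standard.
2. Keep the main per-patient-year rate on the record alone. Do not add CSRI-only contacts to the last six months. Label utilisation and cost as care documented in the study-clinic record, and state whose records criterion 11 was taken to cover.
3. Optionally, give one sensitivity estimate of utilisation and cost, divided by the pooled ratio and not scaled within provider-type-by-country cells. State the assumption that capture late in follow-up also applies to earlier years.

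The cost is one table and a less sweeping claim, from data already planned. The wording change would go through the amendment route in section 18. I would not ask partner centres for visit dates: version 4.0 was signed in December 2022 with recruitment expected to end in Q1 2023, so that would change data collection late and partly duplicate the device fields in Appendix 1.
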